# HEALTH RESEARCH PROJECT APPLICATION REPORT

**Title:** Evaluation of the ability of the MEESSI-AHF scale to improve decision making and prognosis in patients diagnosed with acute heart failure in the emergency department

**Clarification:** This is the complete protocol granted by Instituto de Salud Carlos III (Spanish Ministry of Health), and the study that applies to Clinicaltrials.gov registry is only the Study 3 of the present protocol

## BACKGROUND AND CURRENT STATUS OF THE TOPIC

---

*Purpose of the project, background and current state of scientific-technical knowledge, national or international groups working in the specific line of the project or in related lines. International groups working in the specific line of the project or in related lines. Cite references in the following section: Most relevant bibliography.*

Acute heart failure (AHF) is one of the main causes of hospitalization in Spain (1) and represents one of the greatest economic and health care burdens in any public health care system (2,3). It is associated with high in-hospital and post-discharge mortality and high readmission rates. In Spain, as in many countries with a public health system, the vast majority of patients with AHF are initially attended in hospital emergency departments (ED). Thus, AHF is one of the most frequent diagnoses in the ED; and in Western countries between 3% and 5% of hospital admissions are for AHF, mostly in cardiology and internal medicine departments. In the population over 65 years of age, it is the leading cause of hospitalization and is responsible for 2% of total health care expenditure (1-4).

However, not all patients diagnosed with AHF in the ED are hospitalized. Depending on the country, its healthcare system and the organization of its ED, between 18% and 36% of patients with AHF are discharged directly from the ED after a variable period of observation (5-7). Several studies have shown that this decision can lead to an increased risk of adverse events for the patient, either in the form of a return visit to the ED or hospitalization or even death (6). An important element contributing to this increase in adverse events is the lack of risk stratification of patients with AHF in the ED prior to the decision to discharge or admit them, as is done in other circumstances such as acute coronary syndrome (9) or pneumonia (10). To date, only 3 risk scales have been available to be applied to patients with AHF to aid the ED physician's decision making, two developed in Canada (EHMRG (11) and OHFRS (12)) and one in the United States (STRATIFY (13)). Their application in these countries is scarce, and they have not been implemented in Spain to date. In fact, it is possible that their application to AHF patients seen in Spanish EDs may be suboptimal. Thus, when we evaluated the discriminative capacity of the Canadian EHMRG scale in Spain, we observed that it decreased substantially (from an area under the receiver operating characteristic -COR- curve -ABC- of 0.807 in the original study to 0.741 in the Spanish population) (14). The rest of the risk stratification scales that have been described in the literature have been derived from patients hospitalized for AHF and, therefore, are not applicable in the ED where, as mentioned above, between 18%-36% of patients with AHF are discharged without hospitalization.

In this regard, our group has just derived and validated the MEESSI-AHF scale from 8,096 patients with AHF diagnosed in 34 Spanish EDs. The MEESSI-AHF scale is thus the fourth risk scale to be applied in the ED in patients with AHF, since, like the previous three, it has been developed from the entire universe of patients diagnosed with AHF in the ED, including those admitted and discharged home without admission. The MEESSI-AHF scale stratifies risk based on the probability of death during the 30 days following diagnosis of AHF in the ED. It has a high discriminative power, the best among those published and

discussed in the previous paragraph (11-13), with an ABC COR of 0.836 in the referral cohort and 0.828 in the validation cohort. For a comparison of the main characteristics of the four currently existing scales (STRATIFY, OHFRS, EHMRG and MEESSI-AHF), see the Figure included in the appendix.

The MEESSI-AHF scale proposes a clinical classification into four risk groups: low, medium, high and very high, with all-cause mortalities 30 days after the index event (ED visit) estimated at around 2%, 7%, 15% and 45% for each risk group, respectively. To calculate risk, the scale uses 13 variables available during the patient's first ED visit. This calculation is also facilitated by a freely available online calculator (<http://meessi-ahf.risk.score-calculator-ica-semes.portalsemes.org/>). Furthermore, the development of the scale provides 7 additional mathematical models to the complete model that allow the calculation of risk even in the absence of 3 of the 13 variables that make up the MEESSI-AHF scale (Barthel index of the patient at the ED, troponin and NT-proBNP, in any combination). The MEESSI-AHF scale proposes that those patients classified as low risk would be ideal for the emergency physician to proceed to direct discharge without hospitalization, since the expected mortality in these patients during the following 30 days is very low (around 2% overall).

Subsequently, we revalidated the MEESSI-AHF scale in a new population of 4711 AHF patients from 30 Spanish EDs. Again, the discriminative ability of the scale was very good (ABC ROC of 0.810) and, more importantly, this ability was similar and without significant differences in university and county hospitals, in EDs with different activity loads, and in those EDs that had previously participated in the original development of the scale and those that had not (unpublished data). In the latter, which was a group of 10 EDs that included patients for the first time, the ABC COR was 0.832. In total, therefore, 41 HEDs have already been involved in the MEESSI-AHF scale development project, which represents 12% of the 339 hospitals in the Spanish public health system.

Therefore, we believe that the MEESSI-AHF scale is ready to face the challenge of trying to effectively help emergency physicians in the decision-making process (discharge or admission) of patients with AHF attended in these departments. The scale could have a double positive impact on AHF patients. On the one hand, it could contribute to improving prognosis in a syndrome, that of AHF, whose prognosis has not changed over the last decades and in which attempts to find pharmacological interventions with positive results have failed (16-18). On the other hand, it could contribute to an improvement in the efficiency of the system by identifying low-risk patients who can potentially be managed on an outpatient basis, without admission, if the results obtained in them are shown to be good. Thus, a percentage of hospital admissions would be avoided.

Ideally, if the decision making made by the emergency physician in current routine clinical practice is correct, the distribution of risk groups in discharged and admitted patients should be markedly different: among the former, low-risk patients should predominate, while among the latter, low-risk patients should be scarce and medium-, high- and very-high-risk patients should predominate. However, this is currently unknown. Secondly, it is important to verify that patients who are classified as low risk by the MEESSI-AHF scale and, as recommended, are discharged, have acceptable adverse event rates, ideally within the recommended standards (19). This has not been proven either, since during the development of the MEESSI-AHF scale only 30-day mortality was used as an adverse event, and furthermore the risk was calculated globally for each risk category, without distinguishing between patients who were discharged and those who were admitted. Recently, an international consensus document has published quality standards to be achieved in the ED for patients with AHF. Specifically, it has proposed a 30-day mortality of less than 2% for patients discharged without hospitalization from the HED with the possibility of maintaining the patient under observation for a period of 24 hours (a circumstance that occurs in most Spanish HEDs), a rate of revisit to the ED for persistence or worsening of AHF during the following 7 days of less than 10% and a rate of revisit to the ED or hospitalization for the same reason at 30 days of less than 20% (19). From the clinical point of view, the low-risk patients on the MEESSI-AHF scale would be those most suitable for discharge directly from the emergency department without hospitalization. And if the results observed in them conform to these proposed standards, this scale could be an ideal instrument

to improve the management of AHF patients in the ED in daily practice based on a better selection of the patient who is in a position to be discharged directly from the ED.

However, the most important effect to demonstrate is that the application of ED risk stratification in AHF patients using the MEESI-AHF scale can improve these adverse event rates. This requires an experimental approach, not performed so far on any other scale in this context in which we are developing the present project. Currently, the COACH trial is in its initial patient phase, in which, through a randomized clinical trial, the EHMRG scale is measuring the potential impact of its application in routine clinical practice in EDs in the province of Ontario, Canada (20). This trial is scheduled to be completed by the end of 2019. In addition, the same group of investigators has the ACUTE study underway in which they are validating a new model of the EHMRG scale based on 7- and 30-day mortality (21). We believe that it is a priority objective to complete a similar clinical trial with the MEESI-AHF scale so that our scale, developed in Spain, can be competitive with the EHMRG scale and, if the results are favorable, can become the scale of choice for use in the ED in Spain and, eventually, in the EDs of other countries.

Therefore, it is the set of these current challenges that have been raised in the previous paragraphs that motivate the present research project whose potential impact is expected to be great if the results are satisfactory, especially with regard to improving the prognosis of patients with AHF, through an early intervention in the ED: namely, risk stratification prior to decision making (discharge/admission) that improves the selection of patients with AHF hospitalized and discharged from the ED.

## **HYPOTHESIS**

---

The application in routine clinical practice in Spanish hospital emergency departments (ED) of the MEESSI-AHF scale, which stratifies the risk of patients with acute heart failure (AHF), to assist in the decision to admit the patient to hospital or to discharge the patient directly from the ED, contributes:

- 1.- To the improvement of the results obtained in the globality of patients with AHF attended in the emergency department in terms of reconsultation to the emergency department, need for rehospitalization and mortality.
- 2.- Improvement of the results in the subgroup of patients discharged directly from the emergency department, in terms of reconsultation to the emergency department, need for hospitalization and mortality after discharge from the emergency department.
- 3- Improving the selection of patients to be admitted to the hospital, limiting the admission of low-risk patients, who can be kept under observation in the emergency department for 12-24 hours and discharged without hospitalization.
- 4- Improving efficiency in the use of hospitalization resources.

## **OBJECTIVES**

---

- 1.- To determine the distribution in risk categories according to the MEESSI-AHF scale of AHF patients currently admitted to the hospital from the ED and of patients discharged directly from the ED without admission.
- 2.-To investigate whether the outcomes obtained in patients classified as low risk by the MEESSI-AHF scale and who are currently discharged directly from the ED are close to internationally recommended standards, especially in terms of reconsultation to the ED, need for hospitalization or mortality during the 7 and 30 days following discharge.

3.- To prospectively evaluate whether ED risk stratification in patients with AHF, using the MEESSEI-AHF scale, is able to:

3.A.- Improve short- and long-term outcomes in these patients, both overall and in the subgroup of patients discharged from the ED without hospitalization.

3.B.- Improve the efficiency of the system.

## **METHODOLOGY SECTION**

---

*Design, study subjects, variables, data collection and analysis, and limitations of the study.*

The fulfillment of objectives 1 and 2 will be carried out by means of a single study (STUDY 1) of non-interventional design, with consecutive inclusion of patients in 16 Spanish HEDs, and with a 1-year cohort follow-up. In response to objective 3, two different studies have been designed. The first (STUDY 2) consists of a quasi-experimental before/after study comparing the results obtained in patients with AHF attended in 10 Spanish EDs before and after the implementation of the MEESSEI-AHF scale to stratify the risk of patients with AHF in the ED before the decision to admit or discharge them. The second (STUDY 3) will consist of a multicenter, randomized, open-label, clinical trial comparing the effect of risk stratification of AHF patients in the emergency department using the MEESSEI-AHF scale prior to the decision to admit or discharge the patient.

Ethical aspects: The three studies will be carried out in compliance with the Declaration of Helsinki on research in human beings, the Research Ethics Committees will have been approved and all patients will sign Informed Consent prior to their inclusion in the studies.

### **STUDY 1**

Design: Descriptive, multicenter, non-interventional, with consecutive inclusion of patients and 1-year cohort follow-up.

Study Subjects: All patients older than 14 years who consulted in the 16 participating EDs for symptoms and signs compatible with AHF following the Framingham criteria (Ho et al. Circulation 1993; 88:107-15) will be consecutively included and the diagnosis will be verified by determination of natriuretic peptides (BNP or NT-proBNP) (Ponikowski et al. Eur Heart J. 2016;37:2129-200). Failure to confirm clinical suspicion by natriuretic peptide (because it is not determined or is not above the values considered diagnostic) or if the patient presents an episode of AHF in the context of ST-segment elevation acute coronary syndrome (STEMI) will be exclusion criteria, as in most of these cases the patient is transferred to the cardiac hemodynamics unit with minimal ED intervention.

Variables: As independent variables, more than 40 variables will be collected (see appendix) that a priori can potentially be related to the clinical evolution of patients (demographics, personal history, usual chronic treatment at home, baseline functional status and in the acute episode, clinical, analytical and ECG variables of the patient on arrival at the ED, and treatment and management in the ED, including the final destination of the patient after care -discharge/admission-) that are commonly used by the group in their work (Chest 2017; 152: 821-832; JACC Heart Fail 2018; 6:52-62; Eur J Heart Failure 2017; 19:1205-1209), including those necessary for the calculation of the MEESSEI-AHF scale score and patient stratification (Ann Intern Med 2017; 167:698-705). As outcome variables will be collected: 1) cardiovascular and all-cause mortality during the 30 days and year of the index event (ED consultation); 2) ED reconsultation (without admission) for AHF 30 days post-discharge; 3) hospitalization for AHF 30 days post-discharge; 4) all-cause mortality 30 days post-discharge; 5) the combined variable of 2+3+4 30 days post-discharge, and 6) days alive and out of hospital during the 30 days after the index event. Follow-up will be by telephone call to the patient or family member and consultation of hospital and primary care medical records (informed consent will have been collected for this). The adjudication and validation of the event will be carried out

by the PIs of each center. Given that these are easily objectifiable variables (mortality, admission, emergency consultation), it was not considered necessary for the events to be validated by an external researcher blinded to the MEESSI-AHF application.

Data collection and analysis: Data will be collected on a sheet specifically designed for this purpose, with which the 16 EDs of the participating centers are already familiar due to their previous participation in the EAHFE Registry. To answer Objective 1, the classification variable will be the patient's destination after ED attendance: discharge or admission. In all patients, the MEESSI-AHF score will be calculated retrospectively and they will be classified as low, medium, high or very high risk. The distribution of these risk categories will be compared between both groups (discharge/admission). In addition, the characteristics of low-risk patients in both groups (discharge/admission) will be compared and the propensity for a low-risk patient to be admitted to the hospital will be investigated using multiple logistic regression. The aim is to better understand the factors associated with a likely avoidable hospital admission. On the other hand, medium, high and very high risk patients will be grouped and their characteristics will be compared in both groups (discharge/admission) and the propensity for a medium, high or very high risk patient to be discharged from the emergency department will be assessed by multiple logistic regression. The aim is to better understand the factors associated with probably inappropriate discharges from the ED. For Aim 2, we will compare outcomes obtained in the group of low-risk patients discharged from the ED with published standards: 30-day post-discharge all-cause mortality <2%, 7-day post-discharge ED reconsultation for AHF <10% (this outcome variable will be calculated in this study specifically for this comparison), and 30-day post-discharge ED reconsultation or hospitalization for AHF <20% (Miró et al. Eur J Emerg Med 2017; 24:2-12).

Study limitations: 1) Center selection bias (non-randomized).

## STUDY 2

Design: Quasi-experimental before/after study of the effect of implementing the MEESSI-AHF tool to stratify the risk of AHF patients in the ED. Six EDs participating in Study 1 (pre phase) will participate in the present Study 2. After the conclusion of Study 1, the professionals of the 10 EDs will be trained in the use of the MEESSI-AHF scale to stratify risk (post phase). There will be a digital tablet in a centralized location in the ED exclusively dedicated to the calculation of the MEESSI-AHF score. The calculator, which is also available online (<https://semes.org/calculadora-meessi-ahf>) facilitates scoring and classifies the patient into one of four risk categories: low, medium, high or very high. If the patient's classification is "low risk", the system will make the proposal that the patient can be discharged if he or she has shown improvement after the observation period in the emergency department. The ultimate decision, however, will be made by the attending physician. If the patient is not discharged, the reason for not doing so will be classified as: 1) subjective assessment of severity; 2) difficulty of out-of-hospital medical management; 3) lack of out-of-hospital social support; 4) disagreement with the physician's discharge decision, with family or patient refusal; 5) need for admission for an active medical reason not directly related to AHF; and 6) other situations (note). If the patient's classification is "Medium Risk", "High Risk" or "Very High Risk", the system will make the proposal that the patient should be admitted to the hospital. The final decision, however, will be made by the attending physician. If admission is not carried out, the reason for not admitting the patient will be classified, which may be: 1) subjective assessment of non-severity; 2) decision to limit treatment and follow-up at home; 3) disagreement with the physician's decision to admit, with the decision of the family member or the patient to be discharged; and 4) other situations (note).

Study subjects: The inclusion and exclusion criteria will be the same as for Study 1.

Variables: The independent variables will be the same as in Study 1. There will be two primary outcome variables (PROMs): PROM-1) the 1-year all-cause mortality for the overall patients included in the study (regardless of their risk category); and PROM-2) the combined variable of ED revisit, hospitalization or death at 30 days post-discharge for patients discharged directly from the ED. Secondary outcome variables will be the rest of those mentioned in Study 1. In addition, as a measure of efficiency, the percentage of

patients discharged without admission before and after the intervention with the MEESSI-AHF scale will be counted.

Sample size calculation: Presented with Study 3 (see below).

Data collection and analysis: Presented with Study 3 (see below).

Study limitations: 1) center selection bias; 2) cohort bias.

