### **STUDY 3**

**Design:** Multicenter, randomized, open clinical trial, without pharmacological intervention, in which the effect of risk stratification in the ED of patients with AHF using the MEESSI-AHF scale prior to the decision to admit or discharge will be evaluated compared to standard medical practice (without risk stratification). The 10 EDs in Study 1 that do not participate in Study 2 will participate in the study, in an attempt to limit contamination, and inclusion will be competitive. Randomization will be performed at the individual level, as the low number of participating EDs and the high heterogeneity of ED organizational models and postal care circuits make this more advisable than randomization by center. Randomization will determine the formation of the two arms of the study (1:1): patients assigned to "usual medical practice" (control group, CG) and those assigned to "risk stratification" (intervention group, IG), which will be done by means of a list provided to each center. The training of emergency professionals and the decision proposal provided by the MEESSI-AHF scale will be the same as in Study 2. The final decision on admission or discharge will depend, as in Study 2, on the emergency physician in charge of the patient, and if this decision differs from that proposed by the stratification, the reason will be stated (the same as in Study 2).

**Study subjects:** All patients diagnosed with AHF in the ED and who meet the inclusion and exclusion criteria mentioned in Study 1 will be eligible.

**Variables:** The independent variables will be the same as in Study 1 with the addition of the center and professional variables. The primary and secondary outcome variables will also be the same as in Study 2.

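### Study 3 starts the 30-day clock for secondary outcomes 2 to 5 at discharge, so the overall revisit, rehospitalization and composite comparison has no version anchored at randomization

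*Combined protocol and SAP*

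**What the plan says.** The outcome list is set out once, under Study 1, Variables, and uses two time origins.

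- **From the index visit:** outcome 1, "1) cardiovascular and all-cause mortality during the 30 days and year of the index event (ED consultation"), and outcome 6, "6) days alive and out of hospital during the 30 days after the index event".
- **From discharge:** "2) ED reconsultation (without admission) for AHF 30 days post-discharge; 3) hospitalization for AHF 30 days post-discharge", followed by "4) all-cause mortality 30 days post-discharge; 5) the combined variable of 2+3+4 30 days post-discharge".

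Study 2, Variables, takes the list over: "Secondary outcome variables will be the rest of those mentioned in Study 1". Study 3, Variables, does the same: "The primary and secondary outcome variables will also be the same as in Study 2". The randomized trial therefore has the Study 1 definitions.

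The second primary outcome uses a similar composite but names its population: "the combined variable of ED revisit, hospitalization or death at 30 days post-discharge for patients discharged directly from the ED". The Study 1 list has no such restriction. The natural reading is that outcomes 2 to 5 cover all patients, each timed from their own discharge.

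The intervention acts on disposition. For low-risk patients, Study 2, Design (which Study 3 follows) states that "the system will make the proposal that the patient can be discharged if he or she has shown improvement after the observation period". For the three higher risk groups the system proposes admission.

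No section defines discharge (from the ED or from the ward) for an admitted patient, or says how a death before discharge is handled in outcomes 2 to 5.

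**The concern.** A comparison is protected by randomization only if the population and the start of follow-up are the same in both arms whatever the treatment does. Here both depend on disposition. A patient sent home from the ED is followed over roughly days 0 to 30 from the index visit. An admitted patient enters only after surviving the stay and is followed over a later window: days 8 to 38 for an assumed eight-day stay.

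If the tool sends more patients into hospital, some early events in the intervention arm fall before the clock starts. If it sends more home, the reverse happens. Either way the arms can differ on outcomes 2 to 5 although no patient's course has changed.

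Hypothesis 1 claims improvement in revisits, rehospitalization and mortality for all AHF patients, and objective 3.A repeats the overall claim. Mortality has index-anchored measures. Overall revisits and rehospitalization are measured as events only by outcomes 2, 3 and 5.

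**Working it through.** **1. The plan's own figures.** The sample size section of Study 3 gives 2,027 per arm (30% vs 26%) and 568 (25% vs 18%), two-sided 5%, 80% power. The usual two-proportion formula gives 1,977 and 540. With the continuity correction it gives 2,027 and 568, an exact match. Outcomes 2 to 5 have no sample size, so 2,027 serves here only as the arm size.

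**2. Deaths before the clock starts.** The plan puts ED discharges at 30%, so about 0.70 × 2,027 = 1,419 patients per arm are admitted. In-hospital mortality is not given. At an assumed 4% to 10%, 57 to 142 deaths per arm precede discharge. This is not the bias: it occurs in both arms, and only the difference between arms matters.

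**3. Difference between arms if the tool changes disposition only.** Let *s* be the share of the arm moved, *r* their 30-day mortality and *f* the fraction of those deaths that would fall in hospital. The artefact in outcome 4, as a share of the whole arm, is *s* × *r* × *f*. Take *s* = 5% (assumed), so 0.05 × 2,027 = 101 patients; *r* from the plan's risk groups (Background); and *f* = 30% to 70% (assumed).

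| Patients moved | 30-day deaths among the 101 | Deaths leaving (−) or entering (+) outcome 4 | Points of the arm |
|---|---|---|---|
| Medium risk (7%), home to ward | 7.1 | −2.1 to −5.0 | 0.10 to 0.25 |
| High risk (15%), home to ward | 15.2 | −4.6 to −10.6 | 0.2 to 0.5 |
| Very high risk (45%), home to ward | 45.6 | −14 to −32 | 0.7 to 1.6 |
| Low risk (2%), ward to home | 2.0 | +0.6 to +1.4 | 0.03 to 0.07 |

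These are gross counts. An admitted patient's window runs past day 30, so later deaths enter it and offset part of the loss. The last row shows that the sign reverses when the tool moves patients home.

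**4. The composite.** The documents give no length of stay and no event timing, so this step is illustrative only. Assume a moved patient has a 25% composite risk over days 0 to 30 and an event hazard that declines as exp(−*t*/τ) from the index visit. After a stay of *L* days, the risk in the shifted window is 1 − 0.75^exp(−*L*/τ).

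- *L* = 5, τ = 30 days: exponent 0.846, risk 21.6%, difference 3.4 points per moved patient. With 10% of the arm moved, 0.34 points.
- *L* = 10, τ = 20 days: exponent 0.607, risk 16.0%, difference 9.0 points. With 10% moved, 0.90 points.
- Constant hazard: difference 0.

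The illustrative range is thus 0 to 0.9 points for a 10% shift, or half that for 5%. It does not separate revisits from rehospitalization.

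**The case against.** **The deaths are not lost.** A reader might infer that in-hospital deaths disappear from the trial, so that the tool could seem to save lives by admitting more patients. The documents do not support that. Outcome 1, the one-year all-cause mortality primary outcome and outcome 6 all count them, and a false gain in outcome 4 would be exposed by 30-day mortality in outcome 1. This stands, and it confines the point to outcomes 2, 3 and 5.

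**The large figure is an extreme.** A reader might take 0.7 to 1.6 points as the likely size. That needs all 101 moved patients to be very high risk. About 608 patients per arm go home (0.30 × 2,027), so one in six of them (17%) would have to be very high risk, and the Background says the risk mix by disposition is not yet known. The figure also concerns deaths only, which outcome 1 already measures, and shifts in both directions would partly cancel. This stands.

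**Outcomes 2 to 5 may be meant only for patients sent home from the ED.** That would match the published standards used in Study 1 and would remove the shifted window and the in-hospital deaths. But the list carries no such restriction, while the second primary outcome adds one. Even on that reading, the population would be selected after randomization by the decision the tool influences.

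**The SAP will settle it.** The analysis section defers analysis populations and missing data to a later SAP. It does not defer the time origin, which is already fixed.

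**Index anchoring does not remove all dependence on disposition.** A patient on the ward cannot revisit or be readmitted, so longer stays still lower outcomes 2 and 3. This is correct and shapes the fix.

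**Conclusion.** The point holds for Study 3. The start of follow-up and entry to the risk set for outcomes 2 to 5 are decided after randomization by what the intervention changes. For mortality the plan already has sound alternatives. For overall revisits, rehospitalization and the composite it has none, although it claims an overall effect on them.

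The bias can favour either arm and is probably modest: about 0.10 to 0.25 points on outcome 4 for a 5% shift of medium-risk patients, before any offset. This rests on an assumed shift and an assumed in-hospital share of deaths of 30% to 70%; the very-high-risk case is an upper bound. The size for outcomes 2 and 3 cannot be derived from the documents. As these are unpowered secondary outcomes, this is a cheap improvement and not a flaw in the primary analysis. Selection of the ED-discharged subgroup for the second primary outcome is a separate matter.

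**What to change.** For the randomized comparison in Study 3:

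- Define outcomes 2, 3 and 5 over 30 days from randomization (index ED visit) in all randomized patients.
- Do not count the index admission as an event.
- In outcome 5, count death from any cause, including death in hospital.
- For outcomes 2 and 3, treat death as a competing event and say how.
- Use the 30-day all-cause mortality in outcome 1 in place of outcome 4.
- Define discharge for admitted patients, and keep the post-discharge versions as descriptive results for comparison with the published standards.

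**Cost:** a change of wording, with no change in sample size. The event dates needed are implied by outcomes 1 and 6, but the main text does not state that they are recorded, so the data form should be checked.

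**Downside:** patients with long index stays have less time at risk of a revisit or readmission. Outcomes 2 and 3 then measure total effects that still partly reflect disposition, and should be read alongside outcome 5 and days alive and out of hospital.
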